1.14 Will participants be randomized?

Yes

1.15 Will any of the following be used to collect information from the participant or others?

- Screening questions or screening/eligibility questionnaires
- Surveys
- Questionnaires
- Stimuli
- Any other written assessments

Yes

Attachment Name	Category	Version	Date Attached
[name] Program-Perryville.docx	Subject Data Collection Instruments	1	11/05/18
[name] Program-Piedmont.docx	Subject Data Collection Instruments	1	11/05/18
Stanford Healthy Neighborhood Discovery Tool.docx	Subject Data Collection Instruments	1	11/08/18
[Master] E01 CareMessage Exercise 24 Weeks (v.2) - ENG E01 Accounts Schedule (1).pdf	Subject Data Collection Instruments	1	11/05/18
Telephone Survey 2 Baseline Intervention.docx	Subject Data Collection Instruments	3	05/18/20
Telephone Survey 2 Baseline Control.docx	Subject Data Collection Instruments	3	05/18/20

1.16 Does this project involve creating any audio, video, or photographs?

No

1.17 Does the study include any form of deception (e.g., providing participants with false information, misleading information, or withholding information about certain study procedures)?

Examples:

- Procedure includes a cover story that provides a plausible but inaccurate account of the purposes of the research.
- Participants will be provided with false information regarding the particular behaviors of interest in the research.
- Procedures include a confederate pretending to be another participant in the study.
- Participants will be told that the research includes completion of a particular task, when in fact, that task will not be administered.
- Study is designed to introduce a new procedure (or task) that participants are not initially told about.

No

1.18 Indicate any payments or reimbursements to participants (check all that apply)

- [Gift or Debit Card](#)

1.19 Does this study have a plan to have an individual or committee review combined data from all participants on a periodic basis (such as summary or aggregate safety and/or efficacy data)?

No

1.20 What have you done to minimize any risks?

- No foreseeable risks

1.21 What are the potential benefits related to this project for:

- the participant (if any)
- benefits to society (if any)

An increase in physical activity may lead to improved health. The benefit to society is the project, if successful, has the potential to be scaled-up to reach a larger number of people.

1.22 Provide a summary of the analysis methods you will use, including, if applicable, the data points or outcomes you will analyze.

The intervention is at the community, interpersonal, and intrapersonal levels, and the activity environment is classified at the individual level. The basic model for the individual level analysis is: $Y_{jk} = \alpha_j + \beta I_{jk} + \gamma X_{jk} + \eta Z_{jk} + \theta I_{jk} * E_{jk} + \epsilon_{jk}$; where Y_{jk} is the change in physical activity for subject k in j th community ($j = 1, 2, \dots, 12$), $I_{jk} = 1$ if intervention and 0 otherwise, X = a vector of community level covariates, Z = a vector of individual level covariates (including E_{jk} individual level of activity environment), and $I_{jk} * E_{jk}$ = intervention-by-environment interaction. The parameter α_j is the random intercept, β is the main effect for intervention, and θ is the interaction effect. In this model, β is the expected difference in the physical activity level between intervention and control among those whose physical activity is mainly indoor, and $(\theta + \beta)$ is the expected difference in the physical activity level between intervention and control among those whose physical activity is mainly in the natural environment. Both main and

interaction effects are adjusted for community level and individual level covariates. The primary analyses will be conducted at the end of 1 and 2 year follow-up. In these analyses, baseline physical activity level will be used as one of covariates.

1.23 Provide the rationale or power analysis to support the number of participants proposed to complete this study. This study uses a paired, group-randomized design. By using matching criteria, we will balance potential community-level confounding factors (e.g., community size, poverty level) with a gain in the statistical power [9,10]. Based on the literature, we estimated accelerometer-measured MVPA in the control group at 42.5 minutes per week (m/w). [9] In the intervention group, we assume a 16% increase (42.5*1.16 = 49.3), based on a recent meta-analysis [11]. We used a much larger SD of 16 rather than that reported (6.2) to ensure a sufficient sample size both for testing the intervention effect and for testing the intervention-by-environment interaction (moderation) effect. We assumed ICC estimates in the range of 0.01-0.03, based on our pilot studies and values of ICCs in the literature [12-18]. With 12 communities and an average of 48 study subjects in each (a total of 576 subjects for accelerometry), the study has power >90% with 2-sided $\alpha = 5\%$ to detect the mean difference in MVPA between the control (42.5) and intervention (49.3) groups, using Donner's method [19]. For intervention-by-environment interaction, we assume in the natural environment, the intervention and control difference is 57 m/w versus 44 m/w, and in the indoor environment, the difference is 43 m/w versus 41 m/w. Estimates of interaction are based on our pilot work and existing studies [20]. With a common SD in each of four subgroups = 10, we have 84% power to detect a significant interaction using factorial analysis of variance methods (F-test) adjusting for clustering (ICC = 0.03). Our simulation using two-level mixed effect models also indicates the power to detect the assumed interaction effect >90%. Our sample size is determined for accelerometry subjects at the end of Year 2. With a yearly follow-up rate of 80%, which is achievable given our previous work, we need to enroll 576/0.64 = 900 at baseline for accelerometry. For telephone survey subjects, we need to enroll 900/0.75 = 1,200 at baseline.

1.25 Will any data from this project be stored for use in future research studies?
No

1.26 Does this project involve the collection or use of biological samples or genetic data?
No

1.27 Are you requesting institutional certification to contribute human data or samples to a repository or database for broad sharing (public or restricted access)?
No

2. Participants

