The purpose of the present study is to determine if a multilevel intervention (consisting of community events at local walking trails, formation of walking groups, and text messaging) will increase physical activity among rural residents. Intervention community members will receive the multilevel intervention while control communities will not. In the intervention communities, it is preferable for all participants to partake in all aspects of the intervention; however, not every person will partake in every level. We will create a dose-response variable hypothesizing participants who take part in all aspects of the intervention (i.e., attend walking events, takes part in walking groups, and receives text messages) will increase their physical activity more than people who engage in less of the intervention and those in control communities. As a part of the walking group formation in intervention sites, we will be utilizing the Stanford Healthy Neighborhood Discovery Tool application in order to receive feedback from participants related to the walking trails in their towns.

1.4 Specify your research question(s), study aims or hypotheses:
Test the independent and moderating effects of a multilevel intervention and the community environment on physical activity among rural residents.

1.5 Background and significance and/or Preliminary studies related to this project:
Key informant interviews were conducted in the intervention communities with three groups of people, walking trail users, walking trail non users, and stakeholders. We received feedback on the best methods by which to utilize local walking trails in the communities. Further, participants indicated to us their willingness to partake in future aspects of the study. Walking trail users and walking trail non users may be asked to participate as participants, while stakeholders may be asked to partake in a coalition to partner in increasing physical activity in rural southeast Missouri.

1.6 Literature cited/references (if attaching a grant enter N/A):

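### The moderation model has only a community random intercept; if the natural-minus-indoor difference varies between communities, the standard error of theta is too small and its false-positive rate can exceed 5%

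*Combined protocol and SAP*

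**What the plan says.** Item 1.22 gives one basic model for change in physical activity. Its only random term is the community intercept: "The parameter α_j is the random intercept, β is the main effect for intervention, and θ is the interaction effect". On the moderator it says that "the activity environment is classified at the individual level", and the covariate vector Z is described as "including E_{jk} individual level of activity environment". Environment (E) and its product with intervention therefore have fixed coefficients. The item specifies no random slope, no robust or community-level standard error, and no degrees-of-freedom rule.

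Item 1.7 randomises matched communities, not people. Item 1.4 makes moderation part of the study aim. Item 1.23 gives the interaction its own power statement: 84% from an F-test with a clustering allowance at ICC 0.03. It then adds: "Our simulation using two-level mixed effect models also indicates the power to detect the assumed interaction effect >90" per cent. The random terms of that simulation are not stated. The planning base is: "With 12 communities and an average of 48 study subjects in each (a total of 576 subjects for accelerometry").

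Other items give different sizes: seven communities per arm in item 1.7, and 300 people wearing devices in item 1.13.

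**The concern.** Intervention is assigned to communities, while E differs between people in the same community. Theta therefore compares the within-community natural-minus-indoor differences of one arm with those of the other. The community intercept adds the same amount to both environment groups in a town, so it largely cancels out of that difference. It gives the main effect an allowance for clustering and gives theta almost none.

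The model thus assumes that the difference is the same in every control community, and is that value plus theta in every intervention community. Some variation is plausible, since the programme consists of "community events at local walking trails, formation of walking groups, and text messaging", and trails and groups are local. Any such variation lies between randomised units and belongs in the error term for theta. If it exists and is left out, the confidence interval is too narrow, and chance differences among a dozen or so towns could be reported as moderation, which is one of the study's stated questions.

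**Working it through.** **The plan's own figures (item 1.23).**
- Main effect: 49.3 - 42.5 = 6.8, SD 16, 288 per arm. At ICC 0.03 the design effect is 1 + 47 x 0.03 = 2.41 and SE = 16 x sqrt(2 x 2.41/288) = 2.07, giving power of 90.7%. At ICC 0.01 power is 98.8%. The stated power above 90% reproduces.
- Interaction: (57 - 44) - (43 - 41) = 13 - 2 = 11, SD 10. With four equal cells of 144 (assumed) and design effect 2.41, SE = 10 x sqrt(2.41 x 4/144) = 2.59, giving power of 98.9%. The stated 84% does not reproduce directly and is lower than this result. The environment split and the form of the clustering adjustment are not given.

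**Standard error of theta.** Let J be the number of communities (half per arm), m the people per community, p the share classified as natural, s2 the person-level variance, and tau2 the between-community variance of the natural-minus-indoor difference. One community's difference has variance s2/(m p (1-p)) + tau2. Averaging over J/2 communities per arm and subtracting the arms gives:
- true variance: (4/J) x [s2/(m p (1-p)) + tau2]
- variance reported by the stated model: (4/J) x s2/(m p (1-p))
- ratio: R = 1 + r m p (1-p), with r = tau2/s2
- false-positive rate at nominal two-sided 5%: 2 x [1 - Phi(1.96/sqrt(R))]

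Assumptions: p = 0.5, a two-sided 5% normal test of theta, and r of 0, 1%, 3% or 6%. The documents give no value for r. The 3% borrows the upper intercept ICC in item 1.23. The 6% is what independent 3% community effects in the two environment groups would imply.

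| r | R, 12 x 48 (m p (1-p) = 12) | False positives | R, 14 x 21 (m p (1-p) = 5.25) | False positives |
|---|---|---|---|---|
| 0 | 1.00 | 5.0% | 1.00 | 5.0% |
| 1% | 1.12 | 6.4% | 1.05 | 5.6% |
| 3% | 1.36 | 9.3% | 1.16 | 6.8% |
| 6% | 1.72 | 13.5% | 1.32 | 8.7% |

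**Check by simulation** (REML fit with random intercept only, ICC 0.03, 12 x 48). With no slope variance the rate was 5.4%. At 1% it was 6.3-6.4%. At 3%, three sets of 4,000 runs gave 8.9%, 9.1% and 9.5%, and one set of 3,000 gave 10.8%; 9-10% is a fair summary. At 6% it was 13.1-13.6%. With 14 x 21, sets of 4,000 runs gave 5.4-5.5%, 6.5-7.0% and 8.1-8.7% at 1%, 3% and 6%. A test on the community-level differences held 4.4-6.1% throughout.

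**Power once slope variation is allowed for** (contrast 11, 12 x 48, t-test on 10 df, SE = SD x sqrt((4/12) x (1/12 + r))).
- SD 10: SE is 1.94 at r = 3% (power above 99%) and 2.60 at r = 12% (power above 96%).
- SD 16: SE is 2.67, 3.11 and 3.50 at r = 0, 3% and 6%, giving power of about 96%, 89% and 81%.

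**The case against.** The strongest reply is that the harm is conditional. A reader might infer that the planned p-value and interval for theta are already known to be too optimistic. The documents do not support that: no between-community variance of the environment effect is given, an ICC for community levels says nothing about it, and at zero variance the stated test is valid. This part of the reply stands.

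A reader might also use item 1.23 as proof of a large error. The model's SE is sqrt((4/12) x 97/12) = 1.64 (SD 10, with 3% of the variance in the intercept), against a planning SE of 2.59. Since 1.96 x 1.64/2.59 = 1.24, about 21% of null tests would reject if 2.59 were the true SE. But the design effect of 2.41 is inferred and the stated 84% does not reproduce from it, so the 21% cannot be attributed to the plan. What can be said is that the planning test carries an allowance for clustering that the written model does not carry over to theta.

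Three further points stand in part:
- Item 1.22 calls its model basic, which leaves room for extensions, but specifies none. Nor can it be inferred that the simulation in item 1.23 omitted a slope.
- The 6% case assumes that the two environment groups of a town have unrelated community effects. Positive correlation lowers it.
- Ties among people in one walking group arise below community level and in the intervention arm only, which a common random slope does not model exactly. A comparison using one value per community does absorb such dependence.

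**Conclusion.** The point holds in conditional form. The model in item 1.22 fixes the natural-minus-indoor difference within each arm, and its random intercept does not protect theta if that difference varies between communities. The false-positive rate would then be about 6%, 9-10% and 13.5% at assumed slope variances of 1%, 3% and 6% with 12 x 48, and about 6%, 7% and 8-9% with roughly 300 wearers in 14 communities. At zero slope variance it is 5%. These figures assume an even environment split and a normal test; the slope variances are not taken from the documents.

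The structure of the model is certain; the amount of inflation is not. The problem concerns type I error and interval width. It does not show that the interaction is underpowered at the plan's SD of 10. Label: cheap improvement.

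**What to change.** - Write the model with a community-specific slope for E (alpha_j + delta_j x E_jk + ...), correlated with the intercept, and test theta on between-community degrees of freedom: about 10 for 12 unpaired communities, fewer if pairs are modelled.
- State the fallback in advance. A slope variance estimated from 12 to 14 communities may not converge or may be estimated at zero. In either case keep the community degrees of freedom, or compare arms on each community's baseline-adjusted natural-minus-indoor difference. Weight those differences for the number of people in each environment group, because groups may be small with about 21 wearers per town. This two-stage version approximates the mixed model and is not identical to it.
- Restate the interaction power from the chosen test, giving the assumed slope variance and environment split.
- Reconcile items 1.7, 1.13, 1.22 and 1.23 on 12 versus 14 communities and on 300 versus 576 accelerometry subjects, since both change the size of the problem.

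The cost is SAP wording and a small loss of power. With 12 x 48 and a contrast of 11, power remains above 96% at SD 10. At SD 16 it falls from about 96% to 89% or 81% at 3% or 6% slope variance. No extra data are needed.

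### The coefficient labelled the intervention's main effect is the effect among mainly-indoor participants (planned 2 m/w), and no estimate is defined for the overall 6.8 m/w difference that was powered

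*Combined protocol and SAP*

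**What the plan says.** Section 1.22 gives one analysis model for change in physical activity. It has a random community intercept, the intervention indicator I, community and individual covariates (E among the latter), and the product I×E. It states that "β is the main effect for intervention, and θ is the interaction effect". The following sentence defines β as the "expected difference in the physical activity level between intervention and control among those whose physical activity is mainly indoor", and θ + β as the corresponding difference among those active mainly in the natural environment.

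Section 1.23 plans two tests separately. The SD of 16 was chosen to give enough subjects "both for testing the intervention effect and for testing the intervention-by-environment interaction (moderation) effect". The first power statement (above 90%) is "to detect the mean difference in MVPA between the control (42.5) and intervention (49.3) groups". The second, for moderation, assumes 57 versus 44 m/w in the natural environment, while "in the indoor environment, the difference is 43 m/w versus 41 m/w". It is introduced with its own SD: "With a common SD in each of four subgroups = 10".

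The aim in section 1.4 is to "Test the independent and moderating effects of a multilevel intervention and the community environment on physical activity among rural residents".

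**The concern.** In a model with a 0/1 moderator and its product with treatment, the treatment coefficient is the effect at moderator zero. It equals the overall effect only if there is no interaction. The definitions in section 1.22 make indoor the zero category, and section 1.23 assumes a large interaction, so by the plan's own figures the label and the definition describe different quantities.

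Sections 1.4 and 1.23 treat an overall intervention effect as an aim in its own right. Yet the plan contains no model without I×E, no centring of E and no averaged contrast. An analyst who follows the label would report, as the main effect, the result for the subgroup in which little benefit is expected. The effect used to size the study would have no pre-specified estimate, and the choice among candidate estimates could be made after the data are seen.

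**Working it through.** **Inputs.** From section 1.22: the model and the meanings of β and θ + β, which imply E = 0 for mainly indoor and E = 1 for mainly natural. From section 1.23: cell means 57/44 (natural) and 43/41 (indoor), subgroup SD 10; overall means 49.3/42.5, SD 16; ICC 0.01–0.03; 12 communities × 48 = 576, or 288 per arm; two-sided 5%. The share p active mainly in the natural environment is not given, so it is assumed and varied.

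**1. The plan's own power.** The design effect is 1 + 47 × ICC, which is 1.47 at ICC 0.01 and 2.41 at ICC 0.03. SE = 16 × √(2 × DE / 288) = 1.617 and 2.070. Then 6.8/SE = 4.21 and 3.29, giving normal-approximation power of 98.8% and 90.7%. The stated figure reproduces. With a t reference on 10 df (12 communities less 2) it is 96.5% and 84.1%.

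**2. What the coefficients equal under the plan.** β = 43 − 41 = 2. θ + β = 57 − 44 = 13, so θ = 11. The overall effect is β + pθ = 2 + 11p. It reaches 6.8 at p = (6.8 − 2)/11 = 0.436.

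**3. Power for β and for the overall contrast at p = 0.436.** With equal communities, each having the same environment mix, the estimate of β is the difference between indoor means. With indoor share q = 1 − p = 0.564:

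SE(β) = SD × √(2 × [1 + (48q − 1) × ICC] / (288q)), where 48q = 27.07 and 288q = 162.4.

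For example, at SD 10 and ICC 0.03: 10 × √(2 × 1.782 / 162.4) = 1.481, and 2/1.481 = 1.35. The overall contrast has SE = SD × √(2 × DE / 288), as in step 1.

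| SD | ICC | SE(β) | Power for β = 2 (t, 10 df / normal) | SE(overall) | Power for 6.8 (t, 10 df / normal) |
|---|---|---|---|---|---|
| 10 | 0.01 | 1.246 | 31% / 36% | 1.010 | >99% / >99% |
| 10 | 0.03 | 1.481 | 23% / 27% | 1.294 | >99% / >99% |
| 16 | 0.01 | 1.993 | 15% / 17% | 1.617 | 97% / 99% |
| 16 | 0.03 | 2.370 | 12% / 14% | 2.070 | 84% / 91% |

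**4. Sensitivity to the unstated split.**
- Even split: power for β is 22–33% (SD 10) and 12–16% (SD 16).
- Indoor shares of 30–70%: 17–42% (SD 10) and 10–19% (SD 16).
- Everyone indoors: at most 51% (SD 10) or 24% (SD 16).
- The overall effect shrinks as the indoor share rises. At 70% indoors it is 2 + 11 × 0.3 = 5.3. In the worst case (SD 16, ICC 0.03), 5.3/2.070 = 2.56, a normal power of 73%, against 14–15% for β.

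**5. The pattern that would be reported.** In 20,000 simulated trials per setting (21 of 48 natural in each community, variances known, normal test), β was non-significant while the interaction was significant in 63–73% of trials at SD 10 and 83–86% at SD 16.

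**The case against.** The strongest reply is that the plan never says its primary test is β = 0. Section 1.22 answers a request for a summary, calls the equation basic, and explains in the next sentence what β measures. A careful reader would know it is the indoor effect, and section 1.23 shows that a two-group overall comparison was intended. This is fair as to intent, and it is why the power figures for β are conditional on β being tested. It does not supply the missing estimate: no other model is written, and β is the only quantity called the main effect.

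The figures are also open to challenge.
- SD 16 was planned for the overall comparison, not within subgroups. The SD 10 rows are therefore the planned subgroup case, and the SD 16 rows are a sensitivity range.
- The 43.6% share gives arm means of 41 + 3 × 0.436 = 42.3 and 43 + 14 × 0.436 = 49.1, which are not exactly the planned 42.5 and 49.3. It matches only the difference.
- Baseline activity is a planned covariate. If covariates explained half the variance (an illustration only), power for β at SD 10 would rise to 48–62% by normal approximation, still well below that of the overall contrast.
- Section 1.7 has seven plus seven communities and section 1.13 an accelerometer subset of 300. With 300 people in 14 communities, power for β at SD 10 is 20–24%.

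These points change the exact percentages. They do not change what β estimates or the direction of the gap.

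One further point stands and belongs in the remedy. The plan does not say when E is measured. If it reflects follow-up activity, a trail-based intervention could alter it, and averaging over it or adjusting for it would condition on a post-randomisation variable.

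**Conclusion.** The concern holds and must be fixed. Section 1.22 gives the main-effect label to a subgroup effect with a planned value of 2 m/w, less than a third of the 6.8 m/w behind the power statement, and no estimate of the overall effect is defined. The power statement itself is sound for the overall difference by normal approximation; the labelled coefficient estimates something else.

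If β is tested as labelled, power at the planned subgroup SD is roughly one quarter to one third, against more than 99% for the overall contrast from the same data. The likely report is then a null main effect beside a significant interaction.

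The power figures assume 576 analysed in 12 equal communities and an assumed environment split, and they ignore baseline adjustment and pair matching. The mismatch between label and definition depends on none of these.

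**What to change.** 1. In section 1.22, define the primary intervention effect as the overall intervention–control difference.
2. Name one estimator for it: either the coefficient on I in a model without I×E, or β + θ × mean(E) from the interaction model, with the mean taken over the whole cohort. Centring E at that mean gives the second directly. The two can weight participants slightly differently if the environment mix varies, so choose one in advance.
3. State that E is measured at baseline.
4. Keep the I×E model for the moderation aim, and relabel β there as the intervention effect among mainly-indoor participants.

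The cost is a few sentences of analysis-plan text and one contrast. No new data are needed.

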1.7 Describe EACH of your participant populations

- Include description of any control group(s)
- Specify the Inclusion/Exclusion criteria for EACH group

Intervention community members will be selected from seven communities in southeastern Missouri (n=600). Control community members will be selected from seven communities in southeastern Missouri (n=600). Communities are matched based upon population, demographic makeup, and income; then, randomized to the control or intervention condition. Inclusion criteria for both groups are adults, able to consent (e.g., no known cognitive impairments), able to be physically active, residing in the targeted communities, and willing to complete a telephone survey at three time points.

1.8 Check all materials/methods that will be used in recruiting participants:

- Telephone script
- Website or Social Media (printed pages)
- Word of Mouth/Snowball sampling
- Referral
- Other Methods/Source - Address based sampling, Random digit dialing

Attachment Name	Category	Version	Date Attached
Heartland_Moves_Screenshot.JPG	Recruitment: Website	1	11/05/18
Flyer.rtf	Recruitment Script: Phone	1	03/27/19

1.10 Describe where the consent discussion will occur (check all that apply):

- By phone
- Other - At local events (e.g., health fairs, walking events)

1.11 Participants and/or their legally authorized representative will have (check all that apply to the consent process and explain process in Question 1.12 below):

- As much time as they desire to consider enrolling in the study, including:
 - An opportunity to thoroughly review the consent materials with knowledgeable members of the research team, and with family and/or friends as appropriate
 - Sufficient time to have all of their questions answered

1.12 Provide a description of the enrollment and consent process in sequential order and address EACH of the bulleted points below:

- Describe each study population separately including control population
- Describe when recruitment and consent materials are used
- Indicate how much time individuals will have to consider participation
- If eConsent will be used to obtain an electronic signature, describe how the eConsent will be presented to participants, how their questions will be answered and how the participant will receive a copy of the final, signed consent
- Describe the steps that will be taken by the research team to minimize the possibility of coercion or undue influence during the consent process

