To recruit intervention community participants Washington University in St. Louis (WashU) project staff will reach out via telephone to those walking trail users and walking trail non users to determine their current interest in participating in this study (see section 1.5) using the telephone script. Further, WashU project staff will reach out to stakeholders to determine their interest in being a part of a coalition - in this capacity, project staff will use the informational sheet to reach out to stakeholder constituents to determine their interest in partaking in the study.

Recruitment in control communities is detailed elsewhere. Participants in both intervention and control communities may provide their consent immediately after asking any questions, or project staff can call the potential participant back at a later time (typically within a week). It will be stated to participants that participation is completely voluntary, and they are welcome to withdraw at any time.

1.13 Provide a detailed description in sequential order of the study procedures following the consent process - DO NOT cut and paste from the Consent Document.

Describe study populations separately if they will be participating in different procedures

DESCRIBE:

- Control populations, if applicable
- Any randomization, if applicable
- What participants will be asked to do/what happens in the study (in sequential order)
- The time period over which procedures will occur
- Long-term follow-up and how it occurs

Control and intervention participants will conduct a telephone survey at baseline and one follow-up timepoint (n=1241). A subset recruited from the baseline telephone survey, will wear an accelerometer and global positioning devices for one

week at baseline and one follow-up timepoint(n=300).

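### Sections 1.7, 1.13, 1.22 and 1.23 contradict each other on the number and dates of follow-ups and on the accelerometry number, so the stated primary analyses and power do not match the stated procedures

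*Combined protocol and SAP*

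**What the plan says.** Four current sections bear on this.

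- **Section 1.22 (analysis):** "The primary analyses will be conducted at the end of 1 and 2 year follow-up". This needs two assessments after baseline. No single primary time point is named.
- **Section 1.13 (procedures):** "Control and intervention participants will conduct a telephone survey at baseline and one follow-up timepoint (n=1241"). For the accelerometer and GPS subset, the devices are worn for one "week at baseline and one follow-up timepoint(n=300"). Neither follow-up has a date.
- **Section 1.7 (eligibility):** participants must be "willing to complete a telephone survey at three time points". This fits baseline plus two follow-ups, for the survey. The same section describes seven communities per arm: "Intervention community members will be selected from seven communities in southeastern Missouri (n=600"), with a matching statement for control, so 14 in all.
- **Section 1.23 (power):** "Our sample size is determined for accelerometry subjects at the end of Year 2". The completers are given as "With 12 communities and an average of 48 study subjects in each (a total of 576 subjects for accelerometry"). With 80% follow-up per year, 576/0.64 = 900 are to be enrolled for accelerometry and 900/0.75 = 1,200 for the survey. The stated power is above 90%, two-sided 5%.

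**The concern.** The analysis section promises two primary results, while the procedures section supplies follow-up data for one. This applies to the survey and to accelerometry alike, so the choice of outcome measure does not remove the conflict. The only section that supports a third contact is 1.7, and it speaks of the telephone survey; no section schedules a second accelerometry follow-up, although accelerometry is the measure on which 1.23 is sized.

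Two things are at stake. First, when the primary test takes place is left open and could be settled after data have been seen. Second, 1.13 has 300 people in the accelerometry subset where 1.23 needs 576 completers, so a reader who relies on the stated power is relying on a number that the procedures do not deliver.

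**Working it through.** **Schedule, side by side**

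| Section | Assessments after baseline | Date |
|---|---|---|
| 1.7 | Two implied (three survey time points) | none |
| 1.13 | One, survey and accelerometry | none |
| 1.22 | Two | end of years 1 and 2 |
| 1.23 | Sized on one | end of Year 2 |

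If 1.13 governs and its follow-up is at Year 1, the Year 2 analysis has no data and 1.23 is sized for a date that is not observed. If it is at Year 2, the Year 1 analysis has no data and 1.23 has the right date.

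**Reproducing 1.23.** Two-year retention is 0.80 × 0.80 = 0.64; 576/0.64 = 900; 900/0.75 = 1,200. All are exact.

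Inputs for power, all from 1.23: difference 49.3 − 42.5 = 6.8; SD 16; ICC 0.01 to 0.03; two-sided 5%; J = 12 communities. Equal arms follow from the 600 and 600 in 1.7. With N analysed:

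- Design effect: DE = 1 + (N/J − 1) × ICC
- SE = √(2 × 16² × DE / (N/2))
- Power ≈ Φ(6.8/SE − 1.96)

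For N = 576 there are 48 per community. At ICC 0.01, DE = 1.47 and 6.8/SE = 4.206, so power is 98.8%. At ICC 0.03, DE = 2.41 and 6.8/SE = 3.285, so power is 90.7%. The stated figure above 90% is reproduced.

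**Does the missing date alone cost power?** With 900 enrolled, 900 × 0.80 = 720 remain at Year 1 and 576 at Year 2. For 720, DE = 1.59 and 2.77, and power is 99.5% and 92.9%. Either year stays above 90% by this method.

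**Does the 300 cost power?** Section 1.13 does not say whether 300 is enrolled or analysed. If enrolled, 1.23's retention leaves 300 × 0.80 = 240 at one year or 300 × 0.64 = 192 at two.

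| N analysed (J = 12) | DE, ICC 0.01 / 0.03 | 6.8/SE | Power |
|---|---|---|---|
| 300 | 1.24 / 1.72 | 3.305 / 2.806 | 91.1% / 80.1% |
| 240 | 1.19 / 1.57 | 3.018 / 2.627 | 85.5% / 74.8% |
| 192 | 1.15 / 1.45 | 2.746 / 2.445 | 78.4% / 68.6% |

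With the 14 communities of 1.7 the figures are 91.8% / 82.6% (300), 86.3% / 77.1% (240) and 79.2% / 70.7% (192). Within the 300, moving the date from one to two years costs about 6 to 7 points; the rest of the gap from 576 is due to the number itself.

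**The case against.** Several stronger readings are tempting, and the documents do not support them.

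- *A reader might infer that a primary dataset is certainly missing.* That holds only if 1.13 governs. Section 1.7 fits two survey follow-ups, although it is a willingness criterion and not a schedule. The documents show a contradiction; they do not settle it.
- *A reader might infer that the sizing in 1.23 has no date.* It has one, the end of Year 2, and its arithmetic is exact. What lacks a date is the follow-up in 1.13.
- *A reader might infer that the missing date is what weakens the power.* It is not: 720 or 576 retained from 900 both keep the stated level by the plan's method.
- *A reader might infer that the trial is shown to be underpowered.* The calculation does not go that far. It gives no credit for matching or for the baseline covariate in 1.22, and the documents give no size for either gain. The SD of 16 was chosen well above the reported 6.2; at 6.2 the least favourable case above would have 6.8/SE = 2.445 × 16/6.2 = 6.31, with power near 100%. Section 1.22 also says only physical activity, so the survey sample might carry the analysis.

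In the other direction, the normal approximation is generous with 12 communities. With a t reference on 10 degrees of freedom, power with 576 is 96.5% and 84.1%, and with 240 it is 77.6% and 65.9%.

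What stands of the objection is that the power figures are illustrative and apply to the accelerometry main effect. The contradictions in schedule and number remain, because no section resolves them.

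**Conclusion.** The point holds as an unresolved contradiction among four sections and should be corrected before the plan is relied on.

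On timing: if 1.13 governs, one of two stated primary analyses cannot be carried out, and the documents do not identify it. The single follow-up cannot be matched to the Year 2 date of 1.23.

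On numbers, as a separate matter: 300 in 1.13 against 576 completers and 900 enrolled in 1.23. At ICC 0.03 the power on 1.23's own inputs is about 80% if 300 are analysed and 69% to 75% if 300 are enrolled, so the stated level is not reached under either reading. At ICC 0.01 it is reached only if 300 are analysed (91%). These figures assume the difference and SD of 1.23, its 80% yearly retention applied to the 300, equal arms, a normal approximation, and no gain from matching or baseline adjustment. Using 14 communities raises them by about 1 to 2.5 points and does not change the conclusion.

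**What to change.** 1. Reconcile the number and dates of follow-ups across 1.7, 1.13, 1.22 and 1.23, and put a date on the follow-up in 1.13.
2. In 1.22, limit the primary analysis to a time point at which data are collected. Section 1.23 points to Year 2, subject to the date given in 1.13.
3. State whether 300 is the number enrolled or the number analysed.
4. Reconcile 12 communities (1.22, 1.23) with 14 (1.7).
5. Restate the power in 1.23 for the actual number, date and communities, using 0.80 retention for one year or 0.64 for two if 300 is enrolment. Recheck the interaction power at the same time; it was not reassessed here.
6. If two follow-ups are in fact kept, name one as primary or state a multiplicity rule. Two unadjusted tests at 5% could carry a family-wise error of up to 2 × 5% = 10%; the plan does not say how they would be tested.

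The cost is wording in the four sections and a less favourable stated power. No added enrolment and no second wave are needed for this fix. Restoring 576 completers would be a separate decision. If 300 is enrolment, it means 720 − 300 = 420 more (one year) or 900 − 300 = 600 more (two years). If 300 is the number analysed, enrolment is already 300/0.80 = 375 or 300/0.64 ≈ 469, and the addition is 345 or about 431.
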